- For de-escalation at Level R and thereafter, the next dose level of RP-6306 will be ≥25% lower than the current dose (rounded down based on capsule strength) or de-escalated down to the highest previously tolerated dose based on review of the toxicity patterns by the SRC. In addition to decreasing the daily dose level of RP-6306, de-escalation can involve a reduced frequency of dosing (eg, 3 consecutive days on / 4 consecutive days off or 1 week on / 1 week off).
- Dose escalation of RP-6306 will follow the BOIN criteria as guided by the SRC. RP-6306 can continue with increases of 20% to 50% (R+1).

Intrapatient dose escalation may progress in subsequent patients once the next dose level is cleared by the SRC and the treating physician and the patient agrees that intrapatient dose escalation is desired.

Module 1b:

If tolerability of continuous RP-6306 with FOLFIRI is limiting, Module 1b will be initiated if agreed upon by the SRC. In Module 1b, an intermittent dosing schedule of RP-6306 given 3 consecutive days on / 4 consecutive days off will be tested in combination with FOLFIRI. When Module 1b is initiated, the starting dose of RP-6306 and FOLFIRI will be the same as the highest total daily dose evaluated in Module 1a and will be given to a cohort of N≥2 patients. To allow better dose and schedule exploration early in the development, additional schedules may be evaluated that involve intermittent dosing (eg, 2 consecutive days on / 5 consecutive days off or 1 week on / 1 week off) depending on observed toxicities. The dose of RP-6306 or FOLFIRI will be increased or decreased per BOIN criteria independently of Module 1a until an MTD is established. Dose escalation decisions will be discussed with the SRC after at least 2 evaluable patients completing the first 2 14-day treatment cycles and based on the emerging safety and tolerability profile, and clinical PK/pharmacodynamic data across the entire patient population in Modules 1a and 1b.

In the event Modules 1a and 1b are explored concurrently, the Medical Monitor and SRC will prioritize slot allocation for each module. The highest dose level of RP-6306 in this study will not exceed the MTD of RP-6306 monotherapy identified in the MYTHIC study for a given schedule. The totality of safety, PK, pharmacodynamic, and preliminary efficacy data will be used to select a preferred RP2D and schedule for RP-6306 and FOLFIRI.

QD=once daily.

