Based on the outcome of RP-6306 PK evaluation in the initial dose levels and emerging PK data in the MYTHIC (RP-6306-01) monotherapy study, a consideration for a twice daily (BID; same total daily dose as QD) RP-6306 administration will be discussed with the SRC. The decision to initiate BID dosing will be based on observed patient outcomes (eg, absence of toxicities, tumor response, or other pharmacologic activity) and PK parameters such as, but not limited to, elimination half-life ($t_{1/2}$) is <12 hours or the C_{max} : C_{min} ratio >10 (where C_{min} is the minimum observed plasma concentration within the dosing interval). The same dose escalation/de-escalation criteria will apply for BID dosing cohorts. If BID dosing is initiated, the SRC can elect to continue enrolling patients on a daily dosing arm or cease enrollment on this arm based on the data collected.

Maximum Tolerated Dose:

The BOIN design will be employed to find the MTD of continuous RP-6306 (Module 1a) and, if necessary, intermittent RP-6306 (Module 1b) in combination with FOLFIRI. The target toxicity rate is 25%. The maximum sample size will be 80 patients for dose finding in Modules 1a and 1b combined. DLTs occurring within the first 28-days (2 cycles) will be used to direct MTD finding.

The BOIN design uses the following criteria, optimized to minimize the probability of incorrect dose assignment, to guide dose escalation/de-escalation:

- If the observed DLT rate at the current dose is ≤0.197 (<20%), escalate the dose to 1 of the 2 next higher dose levels (ie, 1 level increase of RP-6306 or 1 level increase of FOLFIRI).
- If the observed DLT rate at the current dose is ≥ 0.298 ($\ge 30\%$), de-escalate the dose to 1 of the 2 next lower dose levels (ie, 1 level decrease of RP-6306 or 1 level decrease of FOLFIRI).
- Otherwise, stay at the current dose.

With the BOIN design, re-escalation after de-escalation is allowed and it is possible to escalate back to a dose level previously declared nontolerated. Prior to re-escalating to a previously nontolerated dose, an intermediate dose level may be explored. The final decision regarding degree of re-escalation will be determined by the SRC based on the totality of the safety and PK data.

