For the purpose of overdose control, doses j and higher levels will be eliminated from further consideration if $Pr(pj > 0.25 \mid data) > 0.95$ and at least 3 evaluable patients have been treated at dose level j, where pj is the true DLT rate of dose level j, j = 1, ..., 5. This posterior probability is evaluated based on the beta-binomial model yj | pj ~ binomial(pj) with pj ~ uniform(0, 1), where yj is the number of patients experienced DLT at dose level j. When the lowest dose is eliminated, stop the trial for

safety. When the lowest dose is eliminated, stop the trial for safety. The above dose escalation/de-escalation and elimination rule can be equivalently presented in Table B, which will be used to conduct the trial.

Table B provides information on the different dose decisions based on number of evaluable patients and the number of DLTs reported. Note, more than 6 patients may be exposed at a dose level to better define the MTD.

 Table B:
 Dose Escalation/De-escalation Rules for the BOIN Design

		Number of Evaluable Patients at Current Dose Level										
Action	1	2	3	4	5	6	7	8	9	10	11	12
↑ if number of DLT ≤	0	0	0	0	0	1	1	1	1	1	2	2
Stay current dose if number of DLT =	NA	NA	NA	1	1	NA	2	2	2	2	3	3
\downarrow if number of DLT \geq	1	1	1	2	2	2	3	3	3	3	4	4
Elim if number of DLT ≥	NA	NA	3	3	3	4	4	4	5	5	6	6

BOIN = Bayesian optimal interval; \(\geq = \text{increase}, \quad = \text{decrease}, \text{DLT} = \text{dose-limiting toxicity}, \\ \text{Elim=eliminate}, \text{NA} = \text{not applicable}, \text{dose cannot be eliminated until at least 3 patients have been treated}

Note: Number of DLT is the number of patients with at least 1 DLT. When none of the actions (ie, escalate, de-escalate or eliminate) is triggered, stay at the current dose for treating the next cohort of patients.

Dose finding starts at Dose Level 1. The steps to implement the BOIN design are described as follows:

- 1. Patients in the first cohort are treated at Dose Level 1. Dose decisions will depend on 2 or more evaluable patients completing the first 2 14-day treatment cycles.
- 2. To assign a dose to the next cohort of patients, conduct dose escalation/de-escalation according to the rule displayed in Table B. When using Table B, please note the following:
 - a. "Eliminate" means eliminate the current and higher doses from the trial to prevent treating any future patients at these doses because they are overly toxic.

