 - b. When we eliminate a dose, automatically de-escalate the dose to the next lower level. When the lowest dose is eliminated, stop the trial for safety. In this case, no dose should be selected as the MTD.
 - c. If none of the actions (i.e., escalation, de-escalation or elimination) is triggered, treat the new patients at the current dose.

- d. If the current dose is the lowest dose and the rule indicates dose de-escalation, treat the new patients at the lowest dose unless the number of DLTs reaches the elimination boundary, at which point terminate the trial for safety.
- e. If the current dose is the highest dose and the rule indicates dose escalation, treat the new patients at the highest dose.
- 3. Repeat Step 2 until the maximum sample size of 36 evaluable patients is reached or stop the trial early if the number of evaluable patients treated at the current dose ≥9 and the decision according to Table B is to stay at the current dose.

After the study is completed, results from all DLT evaluable patients, including the relevant backfill cohorts, will be included to assess the MTD. The dose for which the isotonic estimate of the toxicity rate is closest to and no higher than 30% will be selected as the MTD. This computation can be implemented by the shiny app "BOIN" available at http://www.trialdesign.org. The RP2D for RP-6306 and FOLFIRI will be based on discussion between the Investigators and the Sponsor and will be either the established MTD or a dose lower than MTD based on the totality of the safety, PK, pharmacodynamics, and preliminary efficacy.

Dose-Limiting Toxicity Criteria:

Toxicity will be assessed using the National Cancer Institute (NCI) Common Terminology Criteria for Adverse Events (CTCAE) version 5.0 unless otherwise specified. A toxicity will be considered dose-limiting if it occurs during the first 2 cycles (28 days), meets the predefined criteria for DLT, and is deemed at least possibly related to study treatment. If multiple toxicities occur, the most severe toxicity will be used in the assessment.

A DLT is defined as any of the TEAEs (a TEAE is any event that was not present prior to the initiation of study treatment or any event that worsens in either intensity or frequency following exposure to study treatment and for up to 30 days following the last dose of study treatment) listed below that is not clearly and incontrovertibly due to disease progression or extraneous causes.

DLTs will be defined as any of the following:

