APPENDIX 6. SIMULATED OPERATING CHARACTERISTICS OF DOSE ESCALATION DESIGN

Table 22 shows the operating characteristics of the proposed design for this study with 5 scenarios involving various numbers and locations for the MTDs, based on 5000 simulations using the BOIN Design Desktop Program. The computer simulations allow operating characteristics of the design to be estimated, such as the expected proportion of patients who will be either under- or over-dosed, how accurately the true MTD will be identified and how many patients are expected to be exposed to each dose level. The proportion of patients over-dosed, defined as receiving a dose that had a true dose-limiting toxicity rate of >30%, ranged between 15.6% and 28.5% across all assumed dose-toxicity models. The operating characteristics also shows that the design selects one of the true MTD(s), if any, with high probability and allocates more patients to the dose levels with the dose-limiting toxicity rate closest to the target of 0.25.

Table 1: Operating Characteristics of the Drug Combination BOIN design

	Dose Level			Number of	% Early			
	1	2	3	4	5	6	Patients	Stopping
Scenario 2								
True DLT Rate	0.12	0.25	0.42	0.46	0.51	0.55		
Selection %	24.8	62.4	11.1	1.5	0.1	0.0		0.2
% Pts Treated	27.2	47.9	20.3	3.8	0.7	0.1	21.6	
Scenario 3								
True DLT Rate	0.04	0.12	0.25	0.43	0.53	0.63		
Selection %	1.2	30.9	57.2	10.0	0.6	0.0		0.0
% Pts Treated	7.6	36.2	37.8	15.5	2.7	0.3	24.1	
Scenario 4								
True DLT Rate	0.02	0.05	0.08	0.10	0.25	0.40		
Selection %	0.1	3.7	8.3	22.0	52.0	13.9		0.0
% Pts Treated	1.9	15.6	17.5	25.5	27.7	11.7	28.5	
Scenario 5								

True DLT Rate	0.02	0.04	0.06	0.09	0.11	0.25		
Selection %	0.1	2.0	4.4	9.5	24.2	59.9		0.0
% Pts Treated	1.5	14.4	16.5	18.0	25.1	24.5	27.9	

BOIN=Bayesian optimal interval; DLT=dose-limiting toxicity; Pts=patients.

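### Step 3 does not stop a module when Table B says escalate but no higher dose is open, and the Appendix 6 patient numbers fit a broader stopping rule than the one written

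*Protocol*

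**What the plan says.** The protocol synopsis (Maximum Tolerated Dose) and SAP 3.2.2 give the same algorithm.

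- **Table B (SAP Table 2).** At 9 evaluable patients: 0 or 1 DLT escalate, 2 stay, 3 or more de-escalate. At 12: up to 2 escalate, 3 stay, 4 or more de-escalate.
- **Step 2a.** An eliminated dose and all doses above it are closed to future patients.
- **Step 2e.** "If the current dose is the highest dose and the rule indicates dose escalation, treat the new patients at the highest dose". No stop is attached.
- **Step 3.** Step 2 is repeated up to 36 evaluable patients (per module in the SAP). The only early stop is 9 or more patients at the current dose together with the condition that "the decision according to Table B is to stay at the current dose".

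The ladder has a ceiling, which applies schedule by schedule: "The highest dose level of RP-6306 in this study will not exceed the MTD of RP-6306 monotherapy identified in the MYTHIC study". Irinotecan starts at 180 mg/m², which is also the tabulated maximum for later levels.

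Appendix 6 reports operating characteristics "based on 5000 simulations using the BOIN Design Desktop Program". It does not state the stopping option, the cohort size or the start level.

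**The concern.** The result that most clearly supports a top dose, 0 or 1 DLT in 9 patients, is one that does not end the module. Taken literally, Step 3 keeps adding patients at a dose that cannot be raised, until the count turns into a stay, the decision changes to de-escalate or eliminate, or 36 is reached. The same happens at a dose below an eliminated one.

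Two teams could therefore run the module differently from the same text, one stopping at 9 and the other continuing. If the simulations used the broader rule, the patient numbers and allocation percentages in Appendix 6 do not describe the rule that the study staff are told to follow.

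**Working it through.** **Inputs.** "The target toxicity rate is 25"%. The boundaries are 0.197 and 0.298. A dose is eliminated if Pr(p > 0.25 | data) > 0.95 under a uniform prior, once "at least 3 evaluable patients have been treated at dose level j". The cap is 36. True DLT rates are those of Appendix 6, Scenarios 2 to 5. Cohort size and start level are assumptions, varied below.

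**Boundaries.** With the usual BOIN defaults φ1 = 0.6 × 0.25 = 0.15 and φ2 = 1.4 × 0.25 = 0.35:

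- λe = ln(0.85/0.75) / ln[(0.25 × 0.85)/(0.15 × 0.75)] = 0.1968
- λd = ln(0.75/0.65) / ln[(0.35 × 0.75)/(0.25 × 0.65)] = 0.2984

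These match the protocol and, with the elimination rule, reproduce every escalate, de-escalate and eliminate cell of Table B for 1 to 12 patients. The simulation applies the same formulas beyond 12.

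**When Step 3 can act.** 1/9 = 0.111 is below 0.197 (escalate). 2/9 = 0.222 and 3/12 = 0.250 lie between the boundaries (stay). 2/12 = 0.167 is again escalate. The chance of reading escalate after 9 patients at a dose with true DLT rate p is (1−p)^9 + 9p(1−p)^8:

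| p | 0.05 | 0.10 | 0.15 | 0.25 |
|---|---|---|---|---|
| P(0 or 1 DLT in 9) | 93% | 77% | 60% | 30% |

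**Reproducing Appendix 6.** Stopping rule, start column (1 or 2), cohort size (1, 2 or 3) and cap (30, 36 or 40) were varied, and the leading variants were rerun with 20,000 trials per scenario (standard error about 0.05 patients). The table cannot come from a start in column 1. In Scenario 5 that column holds 1.5% of 27.9 = 0.4 patients, and even one cohort of 2 would be 2/27.9 = 7%. The best fit is a start in column 2, cohorts of 3, a cap of 36, and a blocked move counted as a stay:

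| Mean patients | Sc. 2 | Sc. 3 | Sc. 4 | Sc. 5 |
|---|---|---|---|---|
| Appendix 6 | 21.6 | 24.1 | 28.5 | 27.9 |
| Blocked move counts as stay | 21.5 | 24.1 | 28.6 | 27.8 |
| Step 3 as written | 24.1 | 26.1 | 29.7 | 30.2 |
| Written rule minus Appendix 6 | +2.5 | +2.0 | +1.2 | +2.3 |
| Trials reaching 36, blocked counts as stay | 12% | 18% | 31% | 23% |
| Trials reaching 36, as written | 25% | 30% | 42% | 41% |

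The allocation points the same way. The Scenario 5 share at the top dose is printed as 24.5%; the broader rule gives 24.4% and the written rule 28.9%. Scenarios 2 and 3 are recovered by the eliminated-next-dose case alone (21.6 and 24.1). Scenario 5 also needs the top-dose case (30.2 as written, 28.2 with a top-dose stop only, 27.8 with both).

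**Other settings for the written rule.** A cap of 30, which the documents do not mention, gives 22.5, 24.1, 27.0 and 27.4, off by up to 1.5 patients. Cohorts of 2 from column 2 give 24.7, 26.1, 28.4 and 27.9. That fits Scenarios 4 and 5 on the mean but misses Scenario 2 by 3.1 patients, and allocation shares by up to 12.5 points.

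**Well-tolerated ladder (assumed).** Cohorts of 2 from Level 1, rates rising in equal steps to the top dose:

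| True top-dose DLT rate | 5% | 10% | 15% |
|---|---|---|---|
| 4 levels, as written | 34 | 31 | 28 |
| 4 levels, blocked counts as stay | 17 | 18 | 20 |
| 6 levels, as written | 34.5 | 31.8 | 29.8 |
| 6 levels, blocked counts as stay | 21.8 | 23.4 | 24.8 |

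Under the written rule 89%, 66% and 43% of four-level trials run to 36, against 0% to 2%.

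**The case against.** The strongest reply is that Steps 2a to 2e are notes on how to use Table B. Read with Step 2e, an escalate call at the highest dose means treating at the same dose, which is in effect a stay; after an elimination the dose below becomes the highest one left. The close match with Appendix 6 suggests that this was intended. It does not remove the problem: Step 2e says where to treat the next patients, while Step 3 refers to the Table B decision, and in that cell Table B says escalate.

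Three further points stand.

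- A reader might infer that a dose which cannot be escalated never meets Step 3. The documents do not support that: 2/9 or 3/12 at such a dose is a stay and stops the module. In Scenario 5, 35% of trials under the written rule stop on a stay at the top dose. The gap exists only while Table B reads escalate.
- A reader might infer that the planned sample size is wrong. It is not. Planning rests on the maximum of 36 per module, 80 with replacements and 104 in total, and the written rule never exceeds 36. The protocol also allows extra patients at a dose to define the MTD better.
- The ladder is not fixed. An intermediate level may be explored before re-escalation to a dose that was not tolerated, which softens the eliminated-dose case but not the top-dose case.

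**Conclusion.** The point holds: Step 3 is incomplete as written and should be fixed. It gives no early stop while Table B reads escalate at a dose that cannot be raised, and the Appendix 6 patient numbers do not agree with it at the cap of 36.

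In the printed scenarios the effect is 1.2 to 2.5 patients per module on average, with the share of trials reaching 36 rising by 11 to 18 percentage points. MTD selection is almost unchanged (Scenario 5 top dose 59.5% as written, 59.2% under the broader rule), and the escalation, de-escalation and elimination boundaries are not affected. The excess of 8 to 17 patients under the assumed four-level ladder should not be taken as the expected effect. It requires every dose to be well tolerated, and it falls to about 5 to 13 with six levels.

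That Appendix 6 used a broader rule is inferred from the fit, since its settings are not stated. The fitted cohorts of 3 differ from the minimum of 2 in the text. The fitted start in column 2 differs from a start at Dose Level 1 if column 1 is that level; the appendix does not say whether column 1 is instead a fallback level below it.

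**What to change.** In Step 3 of the protocol and of SAP 3.2.2, replace the stopping condition with: stop when at least 9 evaluable patients have been treated at the current dose and the next cohort would again be assigned to that dose, either because Table B says stay, or because it says escalate and no higher dose is available (highest dose, or next higher dose eliminated). State also whether the mirror case in Step 2d, a de-escalate call at the lowest dose, counts; the simulations cannot show how it was handled.

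Alternatively, keep Step 3 and replace the Appendix 6 figures with those of the written rule.

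Either way, rerun Appendix 6 and state the stopping option, the cohort size, the start level, and which dose level each column represents. Rewording Step 3 alone is not enough. With the reworded rule, a start in column 1 and cohorts of 2, the means are 21.8, 24.5, 27.7 and 26.5, which are still not the printed values.

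The cost is one sentence in each document and one simulation run. The downside of the reworded rule is fewer patients at a well-tolerated top dose, which the approximately 24 planned backfill places can supply.

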
Treatment-related Hematologic TEAEs:

- Grade 4 neutropenia lasting at least 7 days or if granulocyte colony-stimulating factor or granulocyte macrophage colony-stimulating factor is given at any time
- Febrile neutropenia (defined as absolute neutrophil count [ANC] <1000/mm³ with a single temperature of 38.3°C [101°F] or a sustained temperature of 38°C [100.4°F] for >1 hour)
- Grade 4 thrombocytopenia or Grade 3 thrombocytopenia associated with Grade ≥2 bleeding
- Grade 4 anemia or Grade 3 anemia requiring red blood cell (RBC) transfusion per local hospital guidelines

Note: The use of transfusions and hematopoietic growth factors, including thrombopoietin analogues, will be part of the DLT definition if such intervention is required.

Treatment-related Nonhematologic TEAEs:

- Grade ≥3 nausea/vomiting/diarrhea that lasts >3 days despite optimal supportive care
- Any Grade 3 treatment-related TEAE of >24-hour duration
- Any Grade 4 treatment-related TEAE of any duration

TEAEs That Will Not Be Considered a DLT Include the Following:

- Grade ≥3 nonhematologic laboratory abnormalities that are not considered clinically relevant in the opinion of the Investigator or respond to medical intervention
- Grade 3 fatigue with duration <7 days and resolved to Grade ≤2, unless it recurs within the first 2 cycles and is considered drug-related by the Investigator
- Grade ≥3 nausea/vomiting/diarrhea that has not been treated with optimal supportive care

Determination of Dose-Limiting Toxicities:

The population used for determination of DLTs will consist of patients who have met the minimum safety evaluation requirements of the study and/or who have experienced a DLT at any time during the initial 28 days of the study. Minimum safety requirements will be met if, during the first 2 cycles of treatment, the patient receives at least 75% of planned total doses of RP-6306 and 100% of the planned dose of FOLFIRI, completes all required safety evaluations per Schedule of Assessments, and is observed at least until 28 days following the first dose of study treatment.

If a patient withdraws from treatment during the first 2 cycles due to any reason other than DLT and does not meet the minimum requirements for inclusion in the DLT-determining population described above, that patient will be replaced.

Diagnosis and Main Criteria for Inclusion:

Inclusion Criteria:

- Written informed consent, according to local guidelines, signed and dated by the participating

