APPENDIX 1. DEFINITION OF DOSE LIMITING TOXICITY (DLT)

DLTs are defined as follows:

Hematologic AEs:

- Grade 4 neutropenia lasting at least 7 days or if G-CSF or GM-CSF is given at any time
- Febrile neutropenia (defined as absolute neutrophil count [ANC] < 1000/ mm³ with a single temperature of ≥ 38.3 °C[101 °F] or a sustained temperature of ≥ 38 °C[100.4 °F] for > 1 hour)
- Grade 4 thrombocytopenia, or Grade 3 thrombocytopenia associated with Grade ≥2 bleeding
- Grade 4 anemia, or Grade 3 anemia requiring red blood cell (RBC) transfusion per local hospital guidelines

Note: The use of transfusions and hematopoietic growth factors, including thrombopoietin analogues, will be part of the DLT definition if such intervention is required.

Non-hematologic AEs:

- Grade \geq 3 nausea/vomiting/diarrhea that lasts >3 days despite optimal supportive care
- Any Grade 3 treatment-related TEAE of >24-hour duration
- Any Grade 4 treatment-related TEAE of any duration

The following events will not be considered a DLT:

- Grade >= 3 non-hematologic laboratory abnormalities that are not considered clinically relevant in the opinion of the investigator or respond to medical intervention
- Grade 3 fatigue with duration <7 days and resolved to Grade ≤2, unless it recurs within the first cycle and is considered drug-related by the Investigator
- Grade >= 3 nausea/vomiting/diarrhea that has not been treated with optimal supportive care

APPENDIX 2. GYNECOLOGICAL CANCER INTERGROUP DEFINITIONS FOR RESPONSE AND PROGRESSION IN PATIENTS WITH OVARIAN CANCER

For patients with ovarian cancer with elevated CA-125 levels, response evaluation will include cancer antigen 125 (CA-125) in addition to Response Evaluation Criteria in Solid Tumors (RECIST) v1.1 criteria as per Gynecological Cancer Intergroup (GCIG) criteria [Rustin 2011].

Definition of Response by CA-125

- A ≥50% reduction in CA-125 levels from a pretreatment sample. The response must be confirmed and maintained for at least 3 weeks (note that GCIG recommends maintenance for at least 28 days; Patients can be evaluated for a CA-125 response only if they have a pretreatment sample that is at least twice the upper limit of the reference range and within two weeks before starting treatment.
- Intervening samples and the confirmatory sample must be less than or equal to the previous sample (within an assay variability of 10%).
- The date when the CA-125 level is first reduced by 50% is the date of the CA-125 response.

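### As written, the 3-day threshold for nausea, vomiting and diarrhea has no effect on Grade 3–4 DLT calls, and the SAP's fatigue-recurrence window is one cycle where the protocol has two (minor)

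*Protocol*

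**What the plan says.** The Protocol Synopsis (Dose-Limiting Toxicity Criteria) introduces the list with "DLTs will be defined as any of the following". Its nonhematologic part has three items. One is specific to gastrointestinal (GI) symptoms: "Grade ≥3 nausea/vomiting/diarrhea that lasts >3 days despite optimal supportive care". The other two are general and name no symptom. The first of these sets a 24-hour limit at Grade 3: "Any Grade 3 treatment-related TEAE of >24-hour duration". The second sets no time limit at Grade 4: "Any Grade 4 treatment-related TEAE of any duration".

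The list of events that are not DLTs has one entry for these GI symptoms: "Grade ≥3 nausea/vomiting/diarrhea that has not been treated with optimal supportive care". SAP Appendix 1 carries the same three items, including "nausea/vomiting/diarrhea that lasts >3 days despite optimal supportive care", and the same exclusion.

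Both documents also exempt Grade 3 fatigue that lasts under 7 days and resolves to Grade 2 or lower. In the protocol the exemption holds "unless it recurs within the first 2 cycles and is considered drug-related by the Investigator". In SAP Appendix 1 it holds "unless it recurs within the first cycle and is considered drug-related by the Investigator". A cycle is 14 days, and both documents use a 28-day, two-cycle DLT window (Protocol Synopsis, Dose Finding; SAP Sections 4.1 and 7).

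SAP Section 7 takes DLTs from the adverse-event eCRF where the site has marked the event as one. It keeps marked events even if the Safety Review Committee (SRC) did not agree.

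**The concern.** A criterion with its own 3-day threshold suggests that shorter, properly treated GI episodes were meant to be tolerated. The two general items remove that tolerance without saying so. The protocol anticipates such events: its Concomitant Medications text covers loperamide, atropine and antiemetic premedication. Two careful readers could then call the same episode differently, one from the whole list and the other from the item that names the symptom.

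DLT is the primary endpoint for the MTD, and the count of patients with a DLT drives each Table B decision. SAP Section 7 has no step for adding an event that meets the written criteria but was not marked, so an omission at the site could persist into the final count.

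The fatigue mismatch is a plain difference between the two documents, and Appendix 1 also departs from the SAP's own 28-day window.

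**Working it through.** **1. GI items side by side.** Take a treatment-related event in the first 28 days, given optimal supportive care, so that the exclusion does not apply.

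| Event | Under the >3-day item alone | Under the full list |
|---|---|---|
| Grade 3, ≤24 h | not a DLT | not a DLT |
| Grade 3, >24 h to 3 days | not a DLT | DLT (Grade 3 item) |
| Grade 3, >3 days | DLT | DLT (both items) |
| Grade 4, ≤3 days | not a DLT | DLT (Grade 4 item) |
| Grade 4, >3 days | DLT | DLT (both items) |
| Grade 5, >3 days | DLT | DLT (>3-day item only) |

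Every Grade 3–4 event caught by the >3-day item is already caught by a general item. The disputed rows are the second and the fourth. The only thing the >3-day item adds is a Grade 5 event lasting over 3 days, because the general items name only Grades 3 and 4. The supportive-care condition still works, but through the separate exclusion, which says nothing about optimally treated episodes of 1 to 3 days. That exclusion applies from Grade 3 upward, so read literally it also exempts Grade 5.

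**2. Fatigue.** The protocol window is 2 × 14 = 28 days; the Appendix 1 window is 14 days. The documents can differ only for a recurrence on Days 15–28. Taking the recurrent episode as the one classified, it must also be:

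- Grade 3 and drug-related;
- longer than 24 hours, or the Grade 3 item does not reach it;
- shorter than 7 days and resolved to Grade ≤2, or the exemption fails in both documents;
- in a patient with no other DLT, because Table B counts patients with at least one.

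**3. What one changed call does in Table B.** First, the plan's own boundaries. Inputs: target φ = 0.25 (Protocol Synopsis, Maximum Tolerated Dose); φ₁ = 0.6φ = 0.15 and φ₂ = 1.4φ = 0.35, the usual BOIN defaults, assumed because the documents do not state them.

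- λe = ln[(1−φ₁)/(1−φ)] / ln[φ(1−φ₁)/(φ₁(1−φ))] = ln(0.85/0.75) / ln(0.2125/0.1125) = 0.1968 (plan: 0.197)
- λd = ln[(1−φ)/(1−φ₂)] / ln[φ₂(1−φ)/(φ(1−φ₂))] = ln(0.75/0.65) / ln(0.2625/0.1625) = 0.2984 (plan: 0.298)

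Escalating at ≤ λe·n DLTs and de-escalating at ≥ λd·n reproduces those rows of Table B for n = 1 to 12. At n = 6, for example, 6 × 0.1968 = 1.18, so escalate at ≤1; 6 × 0.2984 = 1.79, so de-escalate at ≥2. The table is not in dispute.

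Adding one patient with a DLT:

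- n = 2 or 3, 0 to 1 DLT: escalate becomes de-escalate.
- n = 6, 1 to 2 DLTs: escalate becomes de-escalate; the raw rate goes from 1/6 = 16.7% to 2/6 = 33.3%.
- n = 9, 2 to 3 DLTs: stay, which is the early-stopping condition in Step 3, becomes de-escalate; the raw rate goes from 2/9 = 22.2% to 3/9 = 33.3%.
- n = 4, 5, 7, 8 and 10–12: where one patient changes the action, it moves by one step (escalate to stay, or stay to de-escalate).

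The 33.3% figures lie above the 30% ceiling for the final MTD in the Protocol Synopsis, but they are raw rates at one dose, before isotonic pooling.

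**The case against.** Overlapping sufficient conditions do not contradict each other. The list says any item is enough, so the GI text has one literal answer, the conservative one, and the protocol and SAP agree on it. This stands: the defect is a threshold without effect and an unstated intent, not two incompatible rules.

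Central review is also stronger than the eCRF rule suggests. The Protocol Synopsis (Safety) has the Medical Monitor, the Safety Officer and the SRC evaluate safety throughout, with DLTs named among the assessments. SAP Section 7 gives the criterion-based definition before it turns to the eCRF mark. This too stands and lowers the risk. It does not say which GI rule is meant, or supply a written step for unmarked events.

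The Table B shifts show how sensitive the design is at small n and would follow from any misclassified DLT. That is right; they are not a measure of this defect. On fatigue, sites mark events under the protocol, which is correct, and the SAP reports what was marked, so the Appendix 1 phrase has little route to the count.

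A reader might go further and infer that the DLT count is indeterminate, or that the MTD is unreliable. The documents do not support that: the literal text resolves each case, no misclassified event is shown, and no event frequency is given. A reader might also infer that Grade 4 GI events of up to 3 days must remain DLTs. That is the literal result, but the specific item starts at Grade 3 with no upper limit, so a tolerance covering Grade 4 may have been intended. The documents do not settle it.

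**Conclusion.** Both parts hold, and both are minor. The GI threshold has no effect for Grade 3–4 events. The calls that depend on how it is read are optimally treated, related Grade 3 episodes of more than 24 hours and up to 3 days, and Grade 4 episodes of up to 3 days. The fatigue window in SAP Appendix 1 is an error with a very narrow effect. A single changed call can alter a cohort decision, but no probability can be attached to it from the documents.

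The conclusion rests on the Protocol Synopsis and SAP Appendix 1. The DLT section in the protocol body is not in the public text, so a precedence note there cannot be excluded, although Appendix 1 repeats the items without one.

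**What to change.** (a) In both documents, state the intended GI rule.

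- If the 3-day tolerance governs, insert *other* after *Any*, and *nonhematologic* before *treatment-related*, in the Grade 3 item. State explicitly whether Grade 4 nausea, vomiting or diarrhea of up to 3 days is also tolerated or is a DLT at any duration. That choice is the sponsor's.
- If the general rules govern, delete the >3-day item.

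(b) Separately, state that any treatment-related Grade 5 event is a DLT, and limit the supportive-care exclusion so that it cannot exempt Grade 5.

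(c) In SAP Appendix 1, change the fatigue window to the first 2 cycles.

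(d) List any DLT calls that depend on the wording, including unmarked events. If there are any, show the MTD estimate both ways. Leave past cohort decisions as they are.

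The cost is low for (a) to (c): a few edits to the DLT text in each document. Item (d) takes somewhat more, because someone must judge clinically whether unmarked GI events had optimal supportive care.
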